#### **4) Inclusion and Exclusion Criteria**

##### **Inclusion Criteria:**

The inclusion criteria for this research study are patients that have been confirmed COVID-19 positive on an acute-care, telemetry-monitored, non-ICU unit and are considered hypoxemic. Hypoxemic is defined as experiencing rising oxygen requirements as evidenced by increasing levels of supplemental oxygen (i.e. starting at 1-2 L nasal cannula and increasing oxygen need from that level, up to 6 L on nasal cannula.) The patient must also be conscious and oriented, as well as able to change positions independently (meaning that it would not take an increased amount of energy or effort to position independently. Subjects will be patients 18 years and older. If the patient is unable to speak, read, or write English, an alternative consent in their language will be utilized.

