##### **Exclusion Criteria:**

The exclusion criteria included those that are not COVID 19 positive. Those patients that are COVID -19 positive and in an ICU setting, or in need of ICU level respiratory treatments and interventions would be excluded, as well as those with respiratory distress (defined as immediate need for intubation, respiratory rate over 35, PaCO2 level above 65, and accessory muscle use) or in hemodynamic instability (systolic blood pressure below 90) or arrhythmia. The researchers would also exclude patients that have agitation or who have altered mental status, unstable spine/thoracic injury or recent abdominal surgery, significant pressure ulcers (above stage 1), pregnant patients past the 2nd trimester, and patients that have concerning neurological issues (such as seizures). Patients that are unable to change positions independently will also be excluded.

*Describe how individuals will be screened for eligibility.*

This is a single-center prospective study which will be conducted over a period of 8 months on a telemetry-monitored, acute care unit in a large tertiary teaching hospital in Houston, Texas. Randomized sampling will be used to recruit and consent 96 patients that meet the study inclusion criteria (48 in the intervention group and 48 in the control group). This study will seek approval from the Common Spirit Health Institutional Review Board, and all participants receiving the intervention will be consented (see consent form attached).

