## **8) Procedures Involved**

**Study Design:** This will be a prospective randomized cohort study in which data will be collected for over 14 days or until discharged or transferred to a lower level of care from the telemetry-monitored, acute care unit. Data collected on study participants will include the need for escalating respiratory care as well as length of stay in the acute care unit. Comparative analysis will be conducted with retrospective data collected from hospitalized patients (the control group) with a diagnosis of COVID-19 on a non-ICU acute care, telemetry-monitored unit that meets the hypoxemia criteria, but that will not receive the proning intervention. The data from the control group will be collected by a retrospective chart analysis after 14 days past their discharge date.

On a confirmed COVID-19 non-ICU acute care, telemetry-monitored unit, there will be two sets of patients: patients that will receive the intervention of proning plus standard of care, and patients that receive standard of care, but not the proning intervention. Confirmed COVID-19 positive patients are randomly assigned by bed control to a room upon admission to the unit. Patients will be randomized upon admission to the acute care, telemetry-monitored unit, and selected based

on inclusion criteria. The patients that will be prone will be identified by a door slot "slider" that is purple. Timing devices will be purchased and placed at the nurses' station, and checklists to indicate proning times will be placed inside the room with a patient identification sticker. The researchers will be following the proning protocol for acute care patients provided by CommonSpirit Health (CSH).

Patients will consent to participation (using an approved consent document from the CSH IRB), and an order for the proning protocol will be entered in the EMR by the physician. The patient will be educated about self-proning, and instructed to self-prone every 2 hours. The nursing staff will document patient position on the checklists every 2 hours.

1. Upon initiation of the initial proning, the patient will be monitored by the RN for adverse effects for 15 minutes (such as inability to tolerate position or signs of respiratory distress).

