## **18) Consent Process**

Informed consent will be obtained at the bedside of the patient on the COVID-19 acute care, telemetry-monitored covid positive unit who is assigned to the intervention by a member of the research team. This process will be as follows:

- An order to self-prone and verify consent for proning will be entered into the computer by the doctor.
- The research team member will bring a paper copy of the consent to the patient (copy stored on the unit, attached to this submission), and fully explain the consent.
- The patient will be given the opportunity to ask questions and ask for further clarification.
- At the end of the consent process, the patient will be asked to explain the intervention back to the member getting consent.

This process should take in total about 15 minutes, and will be the same for every patient assigned for the intervention group. The patient will be allowed to decline the intervention.

If the patient cannot speak, read, or write English, an alternative consent will be provided in their language of choice, and consent will be obtained through the facility's interpretation device.

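### Section 8 describes the chart-review controls by hypoxemia alone, which is narrower than the eligibility Section 4 sets for all 96 patients; the two must be reconciled before control charts are selected

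*Protocol*

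**What the plan says.** Section 4 (Inclusion and Exclusion Criteria) defines eligibility for the study without naming an arm. Hypoxemia is one defined element: a rising oxygen need, from 1-2 L up to 6 L by nasal cannula. A further requirement follows: "The patient must also be conscious and oriented, as well as able to change positions independently". The exclusions include agitation or altered mental status, arrhythmia, systolic pressure below 90, recent abdominal surgery and pressure ulcers above stage 1. They also repeat the turning requirement: "Patients that are unable to change positions independently will also be excluded". The screening paragraph of the same section says the study will "recruit and consent 96 patients that meet the study inclusion criteria (48 in the intervention group and 48 in the control group").

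Section 8 (Procedures Involved, Study Design) says where the controls come from. They are hospitalized patients with a COVID-19 diagnosis on a "telemetry-monitored unit that meets the hypoxemia criteria, but that will not receive the proning intervention". On timing and source: "The data from the control group will be collected by a retrospective chart analysis after 14 days past their discharge date". The next paragraph makes a general statement: "Patients will be randomized upon admission to the acute care, telemetry-monitored unit, and selected based" on the inclusion criteria.

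For patients who are to be proned, Section 8 adds that "an order for the proning protocol will be entered in the EMR by the physician". Section 18 (Consent Process) also lists this order. Neither section describes a matching step for controls.

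**The concern.** The Section 8 sentence is the only description of how the control group is assembled, and it applies one element of Section 4. Someone selecting charts from it could accept a disoriented patient on 4 L, or one who cannot turn unaided. The same patient could not enter the prone arm, where a team member meets the patient at the bedside and asks for the intervention to be explained back.

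Such patients would plausibly leave the unit later, which affects the primary outcome, time to discharge to home or lower care (Section 10). They would plausibly also have more pressure injuries and ICU transfers, both secondary endpoints (Section 7). Each effect makes proning look better than it is.

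The imbalance would be hard to detect afterwards. The data items in Sections 8 and 9 are demographics, oxygen saturation, respiratory support, proning compliance, pressure injuries and ICU escalation. None records orientation, mobility or exclusion status.

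**Working it through.** **1. The texts side by side.**

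| Element | Section 4, whole study | Section 8, control description |
|---|---|---|
| COVID-19, non-ICU telemetry unit | required | required |
| Hypoxemia as defined | required | required |
| Oriented, turns independently | required | not mentioned |
| Listed exclusions | apply | not mentioned |

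The Section 4 sentence that covers the 48 controls names the inclusion criteria only. It also speaks of consenting all 96, whereas Section 18 requests a waiver of consent for controls. It is therefore not an exact account of how controls are obtained. No precedence rule says which section governs.

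**2. The plan's own figure.** Section 10 states 48 per arm and 80% power for a 50% decline in time to discharge, by log-rank test. Alpha is not stated; I assume two-sided 5%. With exponential stays the effect is a discharge hazard ratio of 2, and Schoenfeld's formula gives 4 × (1.96 + 0.842)² / (ln 2)² = 65.4, so 66 events. That is 66/96 = 69% of patients with an observed discharge. The protocol gives no event fraction, so its figure is neither confirmed nor refuted, and this point does not depend on it.

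**3. What the narrow wording could do.** From the protocol: 48 per arm, log-rank test, 14 days. Assumed: exponential stays, median 5 or 7 days in eligible patients, censoring at day 14, no true effect, and a share *f* of controls who fail the other criteria and are discharged at *r* times the usual rate. There were 4,000 simulated trials per setting. The table gives the percentage of trials significant in favour of proning (nominal 2.5%).

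| *f* | median 5, *r* = 0.5 | median 5, *r* = 0.33 | median 7, *r* = 0.5 | median 7, *r* = 0.33 |
|---|---|---|---|---|
| 0 | 2.6 | 2.8 | 2.4 | 3.1 |
| 10% | 5.3 | 7.5 | 5.0 | 6.2 |
| 20% | 9.0 | 16.3 | 8.7 | 13.2 |
| 30% | 14.9 | 29.4 | 11.9 | 22.8 |
| 40% | 24.2 | 45.3 | 19.0 | 35.7 |

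**4. Hand check of one cell (*f* = 20%, *r* = 0.5, median 7).** Apparent discharge hazard ratio, prone to control:

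- Day 0: 1 / (1 − 0.2 × 0.5) = 1.11.
- Day 7: still on the unit, eligible 0.8 × 0.5 = 0.400 and slower 0.2 × √0.5 = 0.141. The slower share is 0.141 / 0.541 = 0.261, and the ratio is 1 / (1 − 0.261 × 0.5) = 1.15.
- Day 14: eligible 0.8 × 0.25 = 0.200, slower 0.2 × 0.5 = 0.100, slower share 0.333, ratio 1 / (1 − 0.333 × 0.5) = 1.20.

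The ratio is about 1.15 over the window. With 69.6 events on average, the test statistic shifts by ln 1.15 × √69.6 / 2 = 0.58. The chance of exceeding 1.96 is then P(Z > 1.38), about 8.4%, against 8.7% simulated.

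**The case against.** The strongest reply is that Section 4 already governs. Its criteria are written for the study, its screening paragraph expressly counts the 48 controls among those who meet them, and Section 8 itself says patients are selected on the inclusion criteria. On that reading the hypoxemia phrase is shorthand for patients already eligible, the share of ineligible controls is zero, and no bias arises here. This stands to the extent that the defect is a conflict between sections.

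A reader might go further and infer that controls need only be hypoxemic, or that Section 8 overrides Section 4. The documents support neither.

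A reader might also infer that the physician's order enriches the prone arm for fitter patients. The order is described for proned patients only, but nothing says it is a fitness screen or may be withheld for frailty. The firmer one-sided step is consent ("The patient will be allowed to decline the intervention") set against a waiver for controls. That is a separate matter and is not counted in the figures above.

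Two further points have some force. The simulated sizes rest wholly on assumed shares and rates. The direction is also plausible, not certain: Section 10 counts a move to long-term care as discharge, so some dependent patients could reach the event quickly.

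The objection does not remove the need for action. The only sentence on control acquisition still names one criterion, and the planned data would not show whether the others had been applied.

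**Conclusion.** The concern holds as an inconsistency in control eligibility. Section 8 describes controls more narrowly than Section 4, and nothing in the protocol settles which is to be applied when charts are selected. If the Section 8 wording is used, patients who could not have been proned can enter on the control side only, and the likely bias favours proning on the primary outcome and on two secondary endpoints.

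The documents do not determine its size. Over the assumed range, the chance of a false win runs from about 5% (10% ineligible, half the discharge rate) to about 45% (40% ineligible, 0.33 times the rate, median 5 days), against 2.5%. If Section 4 is applied to controls, the bias from this source is nil. That the prone arm is in fact enriched for fitter patients is a possible consequence of one reading; the protocol does not establish it.

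**What to change.** - In Section 8, replace the reference to the hypoxemia criteria with a statement that controls meet every inclusion and exclusion criterion of Section 4, and make the Section 4 screening sentence name both sets of criteria.
- Assess eligibility at the same time point in both arms, using only information recorded by that time, so that later events in a control's chart cannot influence selection.
- Record each criterion in REDCap for both arms, so that comparability can be shown.
- Keep every eligible prone-assigned patient in the comparison whether or not an order is entered.

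The cost is protocol wording, some more chart abstraction and somewhat fewer eligible controls. Section 18 requests a waiver for controls only, so retaining prone-assigned patients who never reach consent would need that request to cover them. A new prospective bedside form, or a physician sign-off for controls, is more than this defect requires.

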## **5) Number of Subjects**

The sample size will be 96 patients (48 patients in the intervention group and 48 patients in the control group).

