## **9) Data and Specimen Banking**

The data obtained from this study will be basic patient demographics, specifically age and gender, height, weight and ethnicity. The patient medical record number, name, and date of admission/discharge are included as PHI necessary to complete this study. Clinical data to be collected include O2 saturation, respiratory support methods, proning duration/compliance, presence of hospital acquired pressure injuries, and need to escalate care to ICU, including initiation of mechanical ventilation. The REDCap project IDs are 2817 and 3682 for reference.

Upon consent to the study, the patient's medical record number will be recorded as the principal identifier, and the above demographic data will be collected from the electronic medical record. This information will be coded to a personal ID generated by the researchers' REDCap software by the principal investigator or members of the research team. The clinical data obtained during and after the intervention will be recorded from the electronic medical record and also linked to the personal ID in the REDCap software.

The list linking the medical record number to the personal ID will only be handled by members of the research team and will be destroyed electronically upon completion of data collection - approximately 8 months after the initial start of the study. This is to allow for easy access of associated data as the researchers update the ID profiles. All of the members of the research team have completed CITI training, as well as financial conflict of interest records.

The researchers do not anticipate any incidental findings that would impact the outcome of this study or the care of the patient. If the patient started the study and then wished to have their data removed, the patient would communicate that to the nurse assigned, who would then call the principal investigator (number provided to the unit). The investigator would then delete the profile from REDCap and remove the medical record number from the study records.

Data collection will proceed as follows:

1. Every calendar day after the patient has been consented and the intervention is occurring, the nurse assigned to the patient will chart O2 saturation, any presence of hospital acquired pressure injuries, and need to escalate care. This data will be recorded in the electronic medical record, and members of the research team will daily update the REDCap profile with that data.

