## **10) Data Analysis Plan**

Retrospective data analysis will be conducted by the research team with data collected from the electronic medical record as well as the checklists (oxygen saturation, demographics, proning protocol) for both the interventional and control group. See attached documents for consent/proning protocol documents.

This study will be a randomized controlled trial. The primary outcome will be time (days) until discharge from the acute care unit to home or lower level of care (e.g., long-term care), and the primary hypothesis test will compare time-to-discharge between "prone" and "not prone" treatment arms.

A sample size of 48 patients per group (N=96) will provide 80% power to detect a 50% decline in time-to-discharge using a log-rank test.

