## **15) Resources Available**

The members of the research team are [name], [name], [name], [name], [name], and [name].

All team members involved in the study are registered nurses (RNs) with bedside experience in an acute-care facility that provides high acuity patient care. The aforementioned team members have completed CITI training specific to conducting research via IRB approval and oversight under institutional guidelines, policies, and ethics. The members of this research team will be conducting this research for the continuation of evidence based practice amidst the COVID-19 pandemic that will provide much needed guidance for the treatment of the COVID-19 affected population. Each member of the study promotes adequate knowledge of the local study hospital, culture and larger local community.

The feasibility of recruiting the required number of suitable subjects within the agreed recruitment period is to be determined once data collection commences and is currently unknown. This will be addressed knowing that the active COVID-19 population is declining due to increased vaccinations and compliance by the general public with adhering to social distancing and wearing personal protective equipment. Given this, the percentage of potential subjects needing to be recruited will be based on the number of qualified study participants. The researchers estimate that in order to obtain statistically significant results, the sample size will need to be 96 patients minimum, with a goal of 130, splitting evenly into control and intervention groups. The research team will have access to the unit's patients at time of data collection per the unit manager and approval of the facility for the estimated time of data collection.

The research study will take place on a COVID-19, acute care, telemetry-monitored unit.

Each member of the research team is expected to devote time to this research study daily during the data collection period for approximately a half an hour each day. This will entail education of the nursing staff affected and collection of both the electronic and paper records. That process is as follows:

- At the beginning of each day, staff huddles occur on the unit at approximately 6:45 AM. A member of the research team will be present at huddle daily to educate the staff nurses on the proning intervention.

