### ***Waiver or Alteration of the Consent Process***

For our patients assigned to the control group, a waiver of consent will be requested.

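### No described step fixes which un-proned patients form the control arm before the unblinded team can see length of stay, so control selection can depend on the primary outcome

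*Protocol*

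**What the plan says.** - **Source and timing of control data.** Section 8 (Study Design) states: "Comparative analysis will be conducted with retrospective data collected from hospitalized patients (the control group", and then: "The data from the control group will be collected by a retrospective chart analysis after 14 days past their discharge date".
- **Assignment.** The same section says patients are randomized on admission to the unit and selected on the inclusion criteria. The only mechanism it names is bed control's allocation of rooms.
- **Entry into the study record.** Section 9: "Upon consent to the study, the patient's medical record number will be recorded as the principal identifier". The daily updating of the database described there applies to consented patients receiving the intervention.
- **Consent of controls.** Section 18: "For our patients assigned to the control group, a waiver of consent will be requested". The consent process in Section 18 covers only patients assigned to the intervention. Section 4, however, says that all 96 patients will be recruited and consented.
- **Real-time confirmation.** Section 15 describes it for each intervention patient and gives no parallel step for controls.
- **Number of controls.** Section 5: "The sample size will be 96 patients (48 patients in the intervention group and 48 patients in the control group". Section 15: "the sample size will need to be 96 patients minimum, with a goal of 130, splitting evenly into control and intervention groups".
- **Primary outcome.** Section 10: "The primary outcome will be time (days) until discharge from the acute care unit to home or lower level of care".
- **Who reads the charts.** Under Section 8 the research team reviews charts for length of stay. Under Section 15 the same team obtains consent and teaches the intervention. No blinding is described.

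**The concern.** A randomized comparison is protected because arm membership is fixed before the outcome exists. Here that is described for one arm only. A proned patient is identified on the unit, consented, recorded and followed daily. A control, as the text stands, need not be identifiable to the study until a chart is opened at least 14 days after discharge. By then length of stay, ICU transfer and escalation can all be read in that chart. The readers know which arm they are filling, and Section 2 records that they expect shorter stays with proning.

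If more un-proned charts qualify than are needed, some must be left out, and no stated rule decides which. A mild preference for longer stays, even an unintended one, would produce an apparent benefit with no effect of proning. The primary comparison is what is at stake. How and when arm membership is recorded is a matter of trial conduct, so a statistical analysis plan would not normally supply it.

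**Working it through.** **1. The plan's own figure.** Section 10 states: "A sample size of 48 patients per group (N=96) will provide 80% power to detect a 50% decline in time-to-discharge using a log-rank test". If times are exponential, a 50% decline is a discharge rate ratio of 2. At an assumed two-sided 5% level, Schoenfeld's formula gives 4 × (1.960 + 0.842)² / (ln 2)² = 4 × 7.85 / 0.480 ≈ 65.3, so 66 events. That is 66/96 = 69% of patients. With all 96 discharged within the window, power would be 92.4%. The stated 80% therefore fits if about 31% are censored, which the protocol does not say. The power figure neither supports nor weakens the present point, but it supplies the 48 per arm used below.

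**2. When is each arm's membership fixed?**

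| Step | Intervention | Control |
|---|---|---|
| Assignment | On admission, by room (Section 8) | On admission, by room (Section 8) |
| Confirmed on the unit | Yes (Section 15) | Not described |
| Consent | Yes (Section 18) | Waiver requested (Section 18); all 96 consented (Section 4) |
| Entry into the study record | On consent (Section 9) | Trigger does not occur if the waiver is granted |
| Data collected | Daily during the stay (Section 9) | At least 14 days after discharge (Section 8) |

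Only the first step is shared, and no list produced at that step is described that the later chart review would have to follow.

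**3. How many controls?** Section 5 gives 48. Section 15 gives 96 as a minimum and 130 as a goal, split evenly, so 130/2 = 65. The number of charts to take is therefore open between 48 and 65.

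**4. What selection could do.** This is a simulation with no true effect. Assumed inputs: exponential stays with an 8-day median in both arms, whole days, censoring at 14 days, 48 against 48, and a two-sided 5% log-rank test. The 48 controls are drawn without replacement from the qualifying charts, with stays above the median given weight *w* against 1 for the rest. Each entry is the discharge rate ratio and the percentage of trials falsely claiming benefit (6,000 trials per setting; simulation error about 0.2 to 0.5 percentage points).

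| Qualifying charts | *w* = 1 | *w* = 1.5 | *w* = 2 |
|---|---|---|---|
| 48 | 1.01, 2.8% | no choice | no choice |
| 54 | 1.00, 2.6% | 1.05, 4.2% | 1.09, 5.6% |
| 60 | 1.00, 2.8% | 1.09, 5.0% | 1.14, 7.6% |
| 65 | 1.00, 2.7% | 1.10, 5.8% | 1.17, 9.4% |
| 96 | 1.00, 2.6% | 1.16, 8.5% | 1.28, 16.3% |

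The nominal rate is 2.5%. Separate runs of the same model gave 7.8% to 8.7% for 96 charts at 1.5 times, and about 13% to 16.6% at 2 times. A 5-day median at 96 charts and 2 times gave 1.24 and 13.8%, so the result does not hinge on the assumed median.

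**5. How plausible is a surplus?** Under even assignment, having N un-proned charts beside 48 proned patients requires (N − 48)/N of those assigned to proning to be lost through refusal or otherwise. That is 6/54 = 11%, 17/65 = 26% and 48/96 = 50%. The protocol gives no refusal rate. Section 18 does allow patients to decline, and nothing says that a patient who declines cannot be counted as a control.

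**The case against.** The quoted sentence dates the collection of control data, not the choice of control patients. Sections 8 and 18 speak of patients randomized or assigned to control, which suggests membership is settled on admission. Section 4 says all 96 are consented, and in that case the recording trigger in Section 9 would apply to controls too. A reader might infer that no control list will be made, or that the team will choose controls by outcome. The documents support neither: they do not describe a list, which is not the same as excluding one, and nothing suggests an intention to select.

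The surplus is also unproven. Section 15 calls recruitment feasibility unknown and the COVID-19 population declining. If no more charts qualify than are taken, selection among them cannot occur. Pools of 96 need half of those assigned to proning to be lost.

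A reader might further infer that such a bias could never be detected or undone. That is too strong: unit admissions and discharges stay in the electronic record, so qualifying un-proned admissions could be listed again and compared with those used, or all analysed.

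What stands after this is narrower. Being assigned by room does not bind the later chart review unless assignments are written down and the review must follow them, and the protocol requires neither. Section 4 does not settle the matter, because its statement on consent conflicts with Section 18.

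**Conclusion.** The concern holds as a gap in the described procedure. The protocol claims randomization on admission, yet nothing it describes ties the control arm to that randomization before length of stay is visible to an unblinded team, and the number of controls is itself open between 48 and 65. Control selection can therefore depend on the primary outcome. The documents do not show that it will.

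The size is unknown. With above-median stays 1.5 to 2 times as likely to be taken, false claims of benefit run at about 4-9% with 54-65 qualifying charts and about 8-16% with 96, against 2.5% nominal, and there is no such bias without a surplus. Pool size, strength of preference and the 8-day median are all assumptions. Two links are inferences from the text: that controls have no record before chart review (consent is the only stated trigger, and a waiver is sought), and that the team is unblinded (from its role on the unit, with no blinding stated).

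The gap touches the primary comparison and is cheap to close before enrolment, so it should be closed.

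**What to change.** In Section 8:

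- Keep one log for both arms. When a patient is assigned on the unit, write the medical record number, date and time, and assigned arm.
- Add to the same line the date on which the eligibility criteria are first met, judged the same way in both arms and without reference to discharge. This cannot be left to admission alone, because Section 4 defines hypoxemia by an oxygen requirement that rises over time.
- Analyse every logged eligible control, or consecutive eligible controls by assignment date up to a pre-stated number. Reconcile the 48 of Section 5 with the goal in Section 15 when setting that number.
- Freeze the control list before any discharge date or length of stay is abstracted, and allow no chart to be added or dropped afterwards.
- State that patients who decline proning are not moved to the control list.

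Elsewhere, reconcile Sections 4 and 18 on who is consented, and cover the log in the waiver request.

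The cost is one log line per admission, kept by the team member who is already on the unit daily, and a sentence in the waiver request. No extra patients or procedures are needed.
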